9.0 Safety Analyses

9.1 General Considerations

Safety data will be summarized for the Safety Analysis Set. Safety summaries will be presented.

There are two sets of planned safety analysis: safety analysis for the Induction Period, and long-term safety analysis.

Safety Analysis for the Induction Period

Safety analysis for the Induction Period will include reporting of adverse events (AEs), laboratory, and vital signs measurements. Frequency tables of subjects with treatment-emergent adverse events (TEAEs) by system organ class (SOC) and by preferred term (PT) as in the Medical Dictionary for Regulatory Activities (MedDRA) dictionary will be provided. All continuous laboratory parameters and vital signs variables at each visit will also be summarized. Frequency tables of subjects meeting criteria for potentially clinically significant vital sign values and for potentially clinically significant laboratory values will be provided.

Long-Term Safety Analysis

Long-term safety analysis will be performed on all cumulative safety data in Induction Period and Maintenance Period up to data cutoff date for any interim lock as deemed appropriate and final lock.

Long-term safety analyses include reporting of AE rate adjusted by cumulative exposure, descriptive summary in laboratory parameters and vital sign variables, and rate of potentially clinically significant laboratory and vital signs values.

Exposure-adjusted event rate (EAER) will be provided for long term safety analysis. For EAER calculation, the numerator will be the total number of AEs reported for the event (i.e., a subject can contribute more than one event to the numerator) and the denominator

will be the total exposure time among subjects under the treatment. The number of AEs reported (numerator), the total number of years of study drug exposure (denominator calculated as total number of days exposed to study drug (i.e., last dose date – first dose date + 84 days) for all treated subjects divided by 365.25), and the exposure-adjusted AE event rate per 100 patient-years calculated as ([numerator (number of AEs)/denominator] • 100 will be presented.

All continuous laboratory parameters and vital signs variables at each visit will be summarized.

Frequency tables and listings of subjects meeting criteria for potentially clinically significant vital sign values and for potentially clinically significant laboratory values will be provided. Missing safety data will not be imputed.

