## 11 COMPLETION OF THE STUDY

The end-of-study is defined as 84 days after the last subject last dose of ravagalimab.

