2.2 Study Design Overview

This is a Phase 2a, multicenter, single arm, open-label (OL) study to investigate the efficacy and safety of ABBV-323 in subjects with moderate to severe UC who failed prior therapy. The study contains a 35-day screening period, 2 treatment periods, and an 84-day follow up period from the last dose of study drug. The induction period is an open-label 12-week treatment period to evaluate the efficacy, safety, tolerability, PK and RO of ABBV-323 for inducing endoscopic improvement at Week 8. Subjects who achieve

clinical response per Partial Adapted Mayo score at Week 12 may continue into the maintenance period. The maintenance period is an OL 92-week treatment period to assess efficacy and safety for maintenance of response with ABBV-323. An internal data monitoring committee (DMC) will review safety at regular intervals.

Induction Period

Up to approximately 40 subjects will be enrolled in the induction period to receive the following treatment:

- ravagalimab 600 mg intravenous (IV) Week 0; ravagalimab 300mg subcutaneous (SC) Weeks 2, 4, 6, 8, 10.

Prior to protocol Version 4.0 subjects were to be randomized in a 2:1 ratio to the following treatment groups:

[figure not shown]
- Group 1: ravagalimab 600mg intravenous (IV) Week 0; ravagalimab 300 mg subcutaneous (SC) Weeks 2, 4, 6, 8, 10
- Group 2: Placebo IV Week 0; Placebo SC Weeks 2, 4, 6, 8, 10

Maintenance Period

Subjects who enter the maintenance period will receive OL ravagalimab 300mg SC every other week (eow) from Week 12 through Week 102.

The schematic of the study is shown in [Figure 1](#).

Figure 1. Induction and Maintenance Period Schematic

The primary analysis will be performed after all subjects completed the study induction period (i.e., completed Week 12 assessments). The final analysis will be performed after all subjects completed the study maintenance period. There will be no multiplicity control for this proof of concept study.

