9.2.1 Treatment-Emergent Adverse Events

Treatment-emergent AEs are defined as any AE with the onset that is on or after the first dose of study drug to the last dose date prior to cut-off date + 84 days or the cut-off date for database lock, whichever occurs first. Events where the onset date is the same as the study drug start date are assumed to be treatment emergent. All treatment-emergent AEs will be summarized overall, as well as by primary MedDRA SOC and Preferred

Term. The SOCs will be presented in alphabetical order, and the PTs will be presented in alphabetical order within each SOC.

The number and percentage of subjects experiencing treatment-emergent AEs will be summarized.

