9.2.4 Treatment-Emergent Adverse Events per Patient-Years of Exposure

Exposure-adjusted AEs per 100 patient-years will be provided, where AEs per 100 patient-years of exposure are defined as the number of AEs divided by the total exposure in 100 patient-years.

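### The exposure-adjusted event rate in SAP 9.1 has no data cut-off limit on person-time, so the rate is understated at any lock before follow-up is complete

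*SAP*

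**What the plan says.** SAP 9.1, under the long-term safety analysis, defines the EAER. For the count, "the numerator will be the total number of AEs reported for the event", with repeat events in one subject included. The person-time is last dose date minus "first dose date + 84 days) for all treated subjects divided by 365.25". SAP 9.2.4 repeats the rate, "defined as the number of AEs divided by the total exposure in 100 patient-years", under a heading that refers to treatment-emergent events, and adds no limit of its own.

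SAP 9.2.1 sets the treatment-emergent window differently. It runs from first dose "to the last dose date prior to cut-off date + 84 days or the cut-off date for database lock, whichever occurs first".

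On timing, SAP 9.1 applies the long-term analysis to cumulative data "up to data cutoff date for any interim lock as deemed appropriate and final lock". SAP 2.2 plans a primary analysis once every subject has finished Week 12, and then: "The final analysis will be performed after all subjects completed the study maintenance period". Protocol Section 11 adds: "The end-of-study is defined as 84 days after the last subject last dose of ravagalimab".

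**The concern.** The numerator and denominator of a rate should cover the same time. Here the count stops at the cut-off, but each subject's person-time always runs 84 days past the last dose, even when those days lie after the cut-off. A subject still on drug, or less than 84 days past the last dose, then adds time in which no event can appear in the data. The excess is never negative, so this mismatch can only lower a nonzero rate, which is the unfavourable direction for a safety measure.

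Limiting the analysis to data up to the cut-off does not cure this. It settles which last dose date enters the formula; the 84 days are a constant added afterwards. SAP 9.2.1 shows the difference: it already refers to the last dose before the cut-off and still needs its second limit. Section 9.1 lacks that second limit.

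**Working it through.** The plan states no EAER or person-time figure, so there is nothing to reproduce. The check applies the two definitions to the same subjects.

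**Definitions**, with F = first dose, L = last dose, C = cut-off (days):

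- SAP 9.1 as written: L − F + 84
- Matching the SAP 9.2.1 window: min(L + 84, C) − F
- Excess per subject: max(0, L + 84 − C)
- Understatement of the rate: Σ max(0, L + 84 − C) / Σ (L − F + 84)

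The day count follows 9.1, with no extra day added.

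**Single subjects** (exact arithmetic):

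- Week 12 dose on the cut-off date: 84 + 84 = 168 days as written, against 84 in the window. Excess 84.
- Last dose at Week 10, cut-off at own Week 12: 70 + 84 = 154 against 84. Excess 70.
- Completer with last dose at Week 102 (day 714), cut-off at own Week 104: 714 + 84 = 798 against 728. Excess 70.
- Last dose at least 84 days before the cut-off: no excess.

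**Whole cohort** (simulation).

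From the documents: about 40 subjects; dosing every 14 days; last dose at Week 10 for subjects who do not continue; dosing to Week 102 at most for those who do.

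Assumed, because the documents do not give them: uniform entry over 18, 24 or 36 months; 30%, 50% or 70% continuing after Week 12; exponential discontinuation in maintenance at 0, 0.5 or 1.0 per year. Each setting was run 2,000 times. Subjects randomized to placebo before protocol Version 4.0 are not modelled.

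| Accrual | Lock at last subject's Week 12: range of means | Lock at last subject's Week 104: range of means | Week 104 lock: highest 95th percentile |
|---|---|---|---|
| 18 months | 8.6–16.5% | 0.1–0.7% | 1.3% |
| 24 months | 6.9–13.3% | 0.1–0.6% | 1.1% |
| 36 months | 4.7–7.8% | 0.1–0.5% | 0.9% |

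At a lock on the defined end of study, the understatement is exactly zero in every run.

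**Mid-case** at the primary lock (24 months, 50% continuing, 0.5 per year; 5,000 runs): mean 9.87%, 5th to 95th percentile 7.1% to 12.7%. A true 300 events per 100 patient-years would be reported as 300 × (1 − 0.0987) ≈ 270.

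**Accrual shape** at the primary lock (1,000 runs per setting), where U is uniform on 0 to 1:

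- Front-loaded entry (U² × accrual period): 6.5–14.0%, 4.8–10.1% and 3.0–4.6% for 18, 24 and 36 months.
- Back-loaded entry (√U × accrual period): 12.3–20.3%, 10.2–17.5% and 7.5–12.7%.

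**The case against.** The strongest reply is about reach. The EAER is required only at the final lock; interim use is optional, and the Induction Period safety outputs in SAP 9.1 do not include it. The larger percentages therefore describe a table that nothing in the plan schedules. This stands, and it is the main reason the point is minor.

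Two outputs also suggest that the final lock may wait for complete follow-up. SAP 5.0 summarises completion of the follow-up period, and SAP 9.2.2 tabulates deaths more than 84 days after last dose. If the lock does wait, the required EAER has no error. That is an inference, however, because SAP 2.2 ties the final analysis to the end of maintenance.

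A programmer might also truncate unprompted, reading exposure up to the cut-off as the intent. That would give the right answer, but the written formula does not say so.

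A literal reading of the 9.1 numerator could take in events outside the treatment-emergent window, since Protocol 6.1 collects serious events from consent. That would push the rate up. The 9.2.4 heading points to treatment-emergent events, and on either reading no event after the cut-off can be counted.

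The accrual assumptions are soft. Protocol Version 4.0 is dated 29 May 2019, and some subjects were enrolled before it. SAP Version 3.0, dated 10 February 2021, still treats the 40th subject's first dose as a future event (Appendix E4). This suggests accrual longer than about 20 months and makes the 18-month row, the highest, doubtful.

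Finally, 168 against 84 days is the largest gap a single subject can show. It is an illustration, not a typical case.

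**Conclusion.** The concern holds. The mismatch between SAP 9.1 and 9.2.1 is certain from the text, and its effect on the person-time runs one way. The size is uncertain because accrual, continuation and retention are assumed. With uniform entry, an EAER produced at the primary lock would be low by a mean of 4.7% to 16.5%, or 4.7% to 13.3% without the doubtful 18-month row. Front- or back-loaded entry widens the range to 3.0% to 20.3%. The Week 104 figures are expected sizes, not bounds.

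Severity is minor. The rate is descriptive, no decision rule uses it, no comparison of rates across locks is planned, and subject percentages are unaffected.

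**What to change.** In SAP 9.1, define each subject's person-time as min(last dose date + 84 days, cut-off date) − first dose date. This keeps the existing day-count convention and matches the window in 9.2.1. Refer to this definition from 9.2.4.

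The cost is one clause, one cross-reference and one line of code, with no new data. Nonzero rates at a pre-final lock will come out somewhat higher than under the present formula; final-lock rates will barely change or not change at all.

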9.2 Adverse Events

Adverse events (AEs) will be summarized and presented using primary MedDRA System Organ Classes (SOCs) and preferred terms (PTs) according to the version of the MedDRA coding dictionary used for the study at the time of database lock. The actual version of the MedDRA coding dictionary used will be noted in the AE tables and in the clinical study report. Specific adverse events will be counted once for each subject for calculating percentages, unless stated otherwise. In addition, if the same adverse event occurs multiple times within a subject, the highest severity and level of relationship to investigational product will be reported.

9.2.1 Treatment-Emergent Adverse Events

Treatment-emergent AEs are defined as any AE with the onset that is on or after the first dose of study drug to the last dose date prior to cut-off date + 84 days or the cut-off date for database lock, whichever occurs first. Events where the onset date is the same as the study drug start date are assumed to be treatment emergent. All treatment-emergent AEs will be summarized overall, as well as by primary MedDRA SOC and Preferred

Term. The SOCs will be presented in alphabetical order, and the PTs will be presented in alphabetical order within each SOC.

The number and percentage of subjects experiencing treatment-emergent AEs will be summarized.

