## 4.2 Recording Data and Analyses of Safety Findings

---

Adverse events will be coded using the Medical Dictionary for Regulatory Activities (MedDRA). The number and percentage of subjects with treatment-emergent adverse events (i.e., any event that begins or worsens in severity after initiation of study drug through 5 half-lives post-study drug dosing) will be tabulated by primary MedDRA System Organ Class (SOC) and preferred term (PT) and compared between arms using Fisher's exact test. The tabulation of the number of subjects with treatment-emergent adverse events by severity grade and relationship to study drug also will be provided. Subjects reporting more than 1 adverse event for a given MedDRA preferred term will be counted only once for that term using the most severe grade according to the severity grade table and the most related according to the relationship to study drug tables. Subjects reporting more than 1 type of event within an SOC will be counted only once for that SOC.

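### The SAP sets no end to the treatment-emergent window for the induction safety tables, and its stated final-analysis trigger falls 70 days before that window closes for the last completers

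*SAP*

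**What the plan says.** SAP 9.1 states: "There are two sets of planned safety analysis: safety analysis for the Induction Period, and long-term safety analysis". For the first it says: "Safety analysis for the Induction Period will include reporting of adverse events (AEs), laboratory, and vital signs measurements", with frequency tables of treatment-emergent events by system organ class and preferred term. It gives that analysis no data scope. The second does have one: "Long-term safety analysis will be performed on all cumulative safety data in Induction Period and Maintenance Period up to data cutoff date".

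The SAP defines treatment-emergent once, in 9.2.1. Onset must fall from "first dose of study drug to the last dose date prior to cut-off date + 84 days or the cut-off date for database lock", whichever comes first. The Operations Manual (Protocol Appendix F, 4.2) is no tighter at the induction end: "any event that begins or worsens in severity after initiation of study drug through 5 half-lives post-study drug dosing".

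On timing, SAP 2.2 (and Protocol 7.3) says: "The primary analysis will be performed after all subjects completed the study induction period (i.e., completed Week 12 assessments"). The same paragraph adds: "The final analysis will be performed after all subjects completed the study maintenance period". Protocol 11 sets a later point for the study itself: "The end-of-study is defined as 84 days after the last subject last dose of ravagalimab".

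For exposure-adjusted event rates, SAP 9.1 counts each subject's exposure as last dose minus first dose plus 84 days. It sets no limit at the cut-off date.

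**The concern.** The induction tables are built from treatment-emergent events, and the only definition of that term runs on through maintenance for anyone who continues. The primary lock waits for the last subject's Week 12, so earlier responders will already be on maintenance treatment. A programmer must either apply 9.2.1 as written or choose a cut that the plan does not state. Day 85, the day before the first maintenance dose, and last induction dose plus 84 days are all plausible, and they treat the follow-up of non-continuers differently. Because the study is open-label, that choice could be made after events have been seen.

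If the literal window were used, crude induction percentages would depend on the enrolment calendar and on who responded. There is also a treatment-attribution problem. Subjects randomised to placebo before Version 4.0 belong to the Safety Analysis Set (Protocol 7.2, SAP 4.0), and responders among them moved to open-label ravagalimab. An unbounded window would bring their ravagalimab-period events into an induction table.

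At the other end, a final lock taken at the stated trigger would miss most of the 84-day follow-up of the last completers, although the protocol collects adverse events throughout that time.

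**Working it through.** **Schedule.** Study day = 7 × week + 1. This reproduces the stated visit days in Protocol Appendix D, for example Week 12 = Day 85, Week 52 = Day 365 and Week 104 = Day 729.

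**How long the window runs**
- Completer: the last dose is at Week 102, Day 7 × 102 + 1 = 715. The window ends on Day 715 + 84 = 799 (Week 114).
- Subject whose last dose is at Week 10: Day 71 + 84 = 155 (Week 22).
- Induction itself: Day 1 to Day 85, or 84 days. A completer's literal window is 798 days, and 798 / 84 = 9.5 times as long.

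**Could responders be far into maintenance at the primary lock?** Protocol Version 4.0 is dated 29 May 2019, and Protocol 4.1 describes subjects enrolled before it. SAP 3.0 is dated 10 February 2021, and Protocol 7.1 requires the SAP to be final before the Week 12 lock. The two dates are 89 weeks apart. A subject enrolled by the first date who responded and stayed on treatment would have had at least 89 − 12 = 77 weeks of maintenance by the second. The dates on which sites adopted Version 4.0, and the actual accrual, are not given.

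**Illustration of the effect on crude incidence.** Let p(d) = 1 − exp(−λ × d / 365.25), where λ is the first-event rate per patient-year. Let r be the proportion of responders and T the weeks of maintenance each has at the cut-off. Non-continuers are held at 84 days in both columns, so the difference comes from maintenance alone:

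incidence = r × p(84 + 7T) + (1 − r) × p(84)

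For λ = 1, p(84) = 20.5%, p(175) = 38.1% and p(448) = 70.7%.
- r = 0.3, T = 13: 0.3 × 38.1 + 0.7 × 20.5 = 25.8%
- r = 0.5, T = 52: 0.5 × 70.7 + 0.5 × 20.5 = 45.6%

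| Assumed λ | Closed at Week 12 | Literal window, r = 0.3, T = 13 | Literal window, r = 0.5, T = 52 |
|---|---|---|---|
| 0.5 | 10.9% | 14.0% | 28.4% |
| 1 | 20.5% | 25.8% | 45.6% |
| 2 | 36.9% | 44.3% | 64.1% |

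All values of λ, r and T are assumptions.

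**Final-analysis trigger**
- Follow-up elapsed at Week 104: 729 − 715 = 14 days. Remaining: 84 − 14 = 70 days.
- If Week 104 moves within its ±7-day window and the Week 102 dose stays fixed, 63 to 77 days remain.

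**Exposure denominator for a completer locked at Week 104**
- Credited: 715 − 1 + 84 = 798 days. Observable: 729 − 1 = 728 days.
- 798 / 728 = 1.096, an excess of 70 days or 9.6%.
- The mismatch is larger early on. With a last dose at Week 10 and a cut-off at Week 12, 71 − 1 + 84 = 154 days are credited against 85 − 1 = 84 observable (+83%). This matters if the long-term analysis is run at an interim lock, which SAP 9.1 allows.

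**The case against.** The strongest reply is that period and treatment-emergence are separate filters. The protocol uses induction as a bounded term (Weeks 0 to 12), SAP 9.1 sets the induction analysis against one on cumulative data, and SAP 8.1 ends its corticosteroid rule at the close of induction. On that reading a cut is plainly intended. This stands as to intent, and a reader who inferred that the SAP directs maintenance events into the induction tables would go too far. But intent does not supply a rule. SAP 8.1 writes the bound out for efficacy, and nothing equivalent is written for safety.

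A second reply concerns the final analysis. The word after gives an earliest time, not a lock date. SAP 5.0 reports completion of follow-up, SAP 9.2.2 reports deaths more than 84 days after the last dose, and Protocol 7.3 allows additional analyses. So a reader who inferred that follow-up events will be lost would also go too far: the loss is permitted, not prescribed. Even with a lock at the trigger, subjects who reached Week 104 at least 70 days earlier lose nothing. Against this, the primary analysis uses the same form of words as its working trigger, and nothing in the plan ties the final lock to the end of follow-up.

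A third reply concerns importance. A reader might suppose that induction event incidence is the main input to Phase 2b planning. The documents do not say so. They give that role to the interim analysis, which Protocol 7.3 describes as an efficacy analysis, and a data monitoring committee reviews safety separately. This stands.

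**Conclusion.** The point holds as two gaps in specification.

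First, SAP 9.2.1 gives no end for induction treatment-emergent events. Applied literally at the primary lock, it would admit maintenance events of Week 12 responders, and open-label ravagalimab events of former placebo subjects. The direction is certain, since added time cannot lower the number of subjects with an event. The size is not. The upper figures in the table give every responder 52 weeks of maintenance, whereas real entry is staggered, so they are not a forecast.

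Second, the stated trigger for the final analysis falls nominally 70 days before the treatment-emergent window and the end of study are reached for the last completers. If the lock is taken then, their events are truncated while the exposure denominator is not, so their exposure is overstated by 9.6% and the rate is diluted. The pooled effect is smaller, because it depends on how many subjects finish within 70 days of the lock.

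This is a descriptive, single-arm proof-of-concept study, so no test is invalidated. The changes should still be made before the locks, because they settle which events are counted.

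**What to change.** - **SAP 9.2.1:** add a definition for the induction analysis. Onset runs from the first dose to before the first maintenance dose for subjects who continue, and to last dose plus 84 days or the cut-off for those who do not. State that follow-up then differs by response (about 84 days against up to 154), and that the last-enrolled non-continuers may have only 14 of their 84 days observed at the primary lock. Alternatively, add a table restricted to onset by Week 12 for everyone.
- **Long-term analysis:** keep the current definition.
- **Protocol 7.3 and SAP 2.2:** set the final-analysis trigger to completion of, or exit from, the 84-day follow-up by all subjects.
- **SAP 9.1:** cap each subject's exposure for the event rate at the cut-off date, so that numerator and denominator cover the same time.

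The cost is wording, plus a final lock about 70 / 7 = 10 weeks later. No new data or procedures are needed.
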